8.4 Study site and study population

8.4.1 Study site in Zambia

Chipata First Level Hospital is a busy, health facility run by the Lusaka District Health Office serving a population of over 100,000. Chipata averages 400-450 new antenatal patients attending ANC clinic each month with an additional 900-1000 return ANC visits. Similar to other facilities in Lusaka the HIV prevalence in ANC clinic is 10-15%.

8.4.2 Study site in Malawi

Bwaila District Hospital is a high-volume district facility run by the Malawi Ministry of Health. Approximately 1,500 babies are delivered each month at the facility and approximately 500 women present each month for infant immunization visits. Bwaila Hospital has been providing PMTCT services since April 2002. Similar to many parts of Lilongwe, the antenatal HIV prevalence is estimated as high as 13%.

8.5 Recruitment and enrollment procedures

Staff will provide interested participants with additional information and referral to the study. Potential participants will be identified at any point in their pregnancy. All women attending the ANC clinic at enrolling study facilities who meet the eligibility criteria (section 8.3) will be invited to participate in the study. All participants will undergo an informed consent procedure to ensure they are well-informed about the study, its objectives, and its requirements (section 9.2)

8.5.1 Enrollment procedures for Trial 1

Following informed consent, HIV-positive pregnant women eligible for Trial 1 will be enrolled at the same visit. We will collect social, demographic, medical, and behavioral information from all participants. We will obtain from the locator information from the participant, including phone numbers, addresses, and directions. Participants will be randomly assigned to one of two study arms (control or intervention). Statistical software will be used to generate a list of random assignments with a 1:1 ratio, balanced for each site. The randomly generated numbers will be placed in opaque sealed envelopes and sequentially numbered with participant identification numbers.⁷³

8.5.2 Enrollment procedures for Trial 2

Following informed consent, HIV-negative pregnant women eligible for Trial 2 will first undergo screening for HIV and hepatitis B surface antigen (HBsAg). Specimens will be drawn; participants will be asked to return in 1-2 weeks to confirm their eligibility to initiate PrEP. During that return visit, candidates who remain eligible (i.e., do

not meet any exclusion criteria) will be formally enrolled at this visit. Similar to Trial 1, we will then collect social, demographic, medical, and behavioral information from all participants. We will obtain locator information from the participant, including phone numbers, addresses, and directions. Participants will be randomly assigned to one of two study arms (control or intervention). Statistical software will be used to generate a list of random assignments with a 1:1 ratio, balanced for each site. The randomly generated numbers will be placed in opaque sealed envelopes and sequentially numbered with participant identification numbers.⁷³

8.6 Study follow-up

8.6.1 Study procedures for Trial 1

In Trial 1, we plan study visits at enrollment, month 1, month 3, and month 6. The study procedures at each visit are listed in Appendix 1.

Participants will collect ART from the local PMTCT program. At each visit, we will obtain information about adherence, regardless of the randomization arm. Study visits and pharmacy visits will be scheduled to minimize the number of trips needed at the clinic.

At six weeks postpartum, we will collect information about delivery and neonatal outcomes, including HIV status of HIV-exposed infants. For most women, this will occur over the course of their 6-month follow-up; for those who have not yet delivered by the time they reach their primary study endpoint, we will schedule an additional follow-up visit accordingly.

For those in the intervention arm, we will also collect data about the iNSC and adherence supporter strategies

8.6.2 Study procedures for Trial 2

In Trial 2, we have included a screening phase to further assess eligibility. We plan study visits at enrollment, month 1, month 3, and month 6. The study procedures at each visit are listed in Appendix 1.

Because PrEP programs are only beginning to roll-out in Malawi and Zambia, we plan to dispense TDF-FTC on a monthly basis. At these pharmacy visits, we will obtain information about adherence, regardless of the randomization arm. Study visits and pharmacy visits will be scheduled to minimize the number of trips needed at the clinic.

At six weeks postpartum, we will collect information about delivery and neonatal outcomes, including HIV status of HIV-exposed infants. For most women, this will occur over the course of their 6-month follow-up; for those who have not yet delivered by the time they reach their primary study endpoint, we will schedule an additional follow-up visit accordingly.

For those in the intervention arm, we will also collect data about the iNSC and adherence supporter strategies.

For HIV-negative women who test positive for HIV over the course of the study, TDF-FTC will be stopped while the diagnosis is confirmed. We will collect a specimen for HIV RNA concentration (i.e., viral load) and storage for HIV resistance testing. If the HIV diagnosis is confirmed, the participant will complete exit study procedures (i.e., analogous to month 6 visit) and receive a guided referral to the HIV care and treatment clinic at the study clinic site.

8.7 Implementation assessment

8.7.1 Quantitative assessment of iNSC implementation

A core component of our adherence support intervention is iNSC, a patient-centered counseling approach that uses distinct stages to guide the counselor and patient through a semi-structured discussion. Within each, the counselor guides the patient through motivational interviewing and other patient-centered strategies. A standard case report form is used to document steps included in the discussion, as well as important content emerging from exploration of facilitators, challenges, needs and strategies. These instruments are adapted from other large network studies, including IMPAACT 2009 (pregnant and breastfeeding women in sub-Saharan Africa) and ATN 110/113 (men who have sex with men in the US).

While iNSC case report forms have been used to retrospectively assess fidelity, including in ATN 110/113,⁷² this approach has important limitations, including improper, missing, and single reporter (i.e., counselor) documentation. In contrast, we propose to code recorded interviews to assess fidelity. This approach has been used to assess motivational interviewing interventions in numerous settings,^{74,75} including for ART adherence in the US.⁷⁶ However, despite the similarities in the counseling techniques, such methodologies have not been applied to iNSC to date.

We will conduct detailed audits of iNSC sessions for all participants randomized to the intervention arm, in either Trial 1 or Trial 2 (n=150 total). As part of informed consent, we will seek permission to audio-record the discussions to be later reviewed by trained audit nurses. Two reviewers will independently rate the iNSC session according to key domains, providing both objective and subjective measures about the quality of the counseling. Through this process, our audit staff will also assess the appropriateness of documentation in the primary case report forms, including misinformation and missing data. It will also provide important feedback loops to improve counseling over time.

8.7.2 Quantitative assessment of adherence supporter implementation

A second component of our intervention is training for designated adherence supporters. At enrollment, we will ask what key attributes participants look for in an adherence supporter and then collect detailed information about the identified candidate. In most cases, this will be a close friend or family member, including the participant's primary male partner. We will document details about the adherence supporter training itself—the selected venue, preferences for format (e.g., one-on-one vs. group sessions), and completion of key curriculum modules. At each follow-up visit, we will administer a standard questionnaire to all participants (i.e., the index pregnant woman) regarding the adherence support provided by this designated individual. This will include ratings about the adherence supporter intervention along three primary domains: level of engagement of the adherence supporter, relationship dynamics (including trust and confidentiality), and satisfaction with the support provided.

8.7.3 Qualitative assessment of multi-component study intervention

We will conduct semi-structured interviews (SSIs) to explore the acceptability of the multi-component adherence support strategy through the experiences of participants and adherence supporters. We are interested in individual-level engagement with the intervention (including satisfaction with the different components), as well as barriers and facilitators to participation.

We will conduct serial SSIs to gain insight about the study intervention over time. We propose a sample size of up to 40 study participants between the two sites, all randomized to the intervention arm: 20 from Trial 1 and 20 from Trial 2 (Table 3). Three interviews are planned—within four weeks each of the enrollment, 3-month, and 6-month study visits. For individuals who are lost to follow-up or formally withdraw from the study, we will make efforts to trace them and conduct a final exit interview.

Table 3: Sample size for qualitative evaluation

	Participants in Zambia (total interviews)	Participants in Malawi (total interviews)
Trial 1 participants in intervention arm	10 (30)	10 (30)
Trial 2 participants in intervention arm	10 (30)	10 (30)
Total	20 (60)	20 (60)

We will use SSI guides, developed and piloted by our teams in the field, to provide a framework for the discussion. The SSIs will be conducted in rooms at or near the clinic that provide sufficient privacy to ensure confidentiality of information and are quiet enough to enable audio recording of the interviews. Each SSI is expected to last 30-60 minutes. Based on our past experiences in Malawi and Zambia, including from the formative phase of the parent study, the proposed sample size should allow us to reach thematic saturation.

8.8 Study drug

8.8.1 Study drug for Trial 1

In accordance to the eligibility criteria, all HIV-positive participants in Trial 1 will be on first-line ART according to local HIV guidelines. Dispensation of ART will be managed by the local PMTCT/ART program at the study facility. We will collect information about prescribed ART drugs, pharmacy dispensations, and adherence evaluations at short visits on a monthly basis, timed with routine clinic visits.

8.8.2 Study drug for Trial 2

To ensure a consistent medication supply over the 6-month follow-up period, we will provide TDF-FTC for PrEP to all study participants in Trial 2. Packaged product will be dispensed by an on-site study staff. Participants will begin daily administration of TDF-FTC from the day of randomization to 6 months after randomization. The drug will be dispensed on a monthly basis.

Tenofovir disoproxil fumarate (TDF) and emtricitabine (FTC) are antiretroviral agents, indicated and used in combination to reduce the risk of sexually acquired HIV in adults at high risk. Each dose contains 300 mg of TDF and 200 mg of FTC, to be dosed on a daily basis.

TDF is a fumaric acid salt of the bis-isopropoxycarbonyloxymethyl ester derivative of tenofovir. The chemical name is 9-[(R)-2 [[bis[[isopropoxycarbonyl]oxy] methoxy]phosphinyl]methoxy]propyl]adenine fumarate (1:1). It has a molecular formula of C₁₉H₃₀N₅O₁₀P • C₄H₄O₄ and a molecular weight of 635.52. TDF is an acyclic nucleoside phosphonate diester analog of adenosine monophosphate. TDF requires initial diester hydrolysis for conversion to tenofovir and subsequent phosphorylations by cellular enzymes to form tenofovir diphosphate. Tenofovir diphosphate inhibits the activity of HIV-1 RT by competing with the natural substrate deoxyadenosine 5'-triphosphate and, after incorporation into DNA, by DNA chain termination. Tenofovir diphosphate is a weak inhibitor of mammalian DNA polymerases α , β , and mitochondrial DNA polymerase γ .

The chemical name of FTC is 5-fluoro-1-(2R,5S)-[2 (hydroxymethyl)-1,3-oxathiolan-5-yl]cytosine. FTC is the (-) enantiomer of a thio analog of cytidine, which differs from other cytidine analogs in that it has a fluorine in the 5-position. It has a molecular formula of C₈H₁₀FN₃O₃S and a molecular weight of 247.24. It has the following structural formula: FTC is a white to off-white crystalline powder with a solubility of approximately 112 mg/mL in water at 25 °C. The partition coefficient (log p) for emtricitabine is -0.43 and the pKa is 2.65. FTC, a synthetic nucleoside analog of cytidine, is phosphorylated by cellular enzymes to form emtricitabine 5'-triphosphate. Emtricitabine 5'-triphosphate inhibits the activity of the HIV-1 reverse transcriptase (RT) by competing with the natural substrate deoxycytidine 5'-triphosphate and by being incorporated into nascent viral DNA which results in chain termination. Emtricitabine 5'-triphosphate is a weak inhibitor of mammalian DNA polymerase α , β , ϵ and mitochondrial DNA polymerase γ .

8.9 Retention

Once participants are enrolled in the trial, the study team will make efforts to retain them in follow-up to minimize bias associated with loss to follow-up. The study team will closely monitor retention rates and address any issues prospectively. Strategies to minimize attrition include:

- Thorough explanation of the study visit schedule and procedures during informed consent.
- Collection of detailed locator information at enrollment.
- Use of appropriate and timely visit reminder mechanisms (including phone calls and text messages, if participants specifically agree).
- Follow-up after missed visits, including home or alternative, off-site visits where possible.
- Mobilization of trained outreach workers to complete in-person contact with participants at their homes and/or other locations.

If participants elect to discontinue their involvement in the study, we will document their stated reason(s). These will be reported in any reports about the study cohort.

8.10 Safety Monitoring

At each study visit, study staff will evaluate participants for social harms and adverse events (AEs). A social harm will be defined as a non-medical untoward consequence of study participation, including: difficulties in personal relationships, stigma, or discrimination from family or community. An AE will be defined as any untoward medical occurrence in a study participant including any abnormal sign (e.g., abnormal physical exam or laboratory finding), symptom, or disease, temporally associated with the individual's participation in the research, whether or not considered related to participation in the research. In addition to events related to study procedures we can expect that this population of pregnant and postpartum women to experience adverse events unrelated to study procedures, including opportunistic infections, side effects from antiretroviral therapy or other medications, hospitalization, and death.

All adverse events and social harms will be documented, assessed for seriousness / severity, expectedness, and relatedness, and carefully monitored. The severity of events will be graded using the National Institute of Health's Division of AIDS Table for Grading the Severity of Adult and Pediatric Adverse Events. We will also record information on all serious adverse events (SAEs) occurring in participants whether or not they are related to study participation or the study drug, including AEs that:

1. Result in hospital admission (unless hospitalization is preplanned, i.e. for delivery) or prolongation of existing hospitalization
2. Are immediately life-threatening, including drug reactions that necessitate discontinuation of study participation,
3. Cause significant, persistent, or permanent harm or disability, either physical or psychological,
4. Result in death to mother or infant, or
5. Are congenital anomalies or birth defects

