6.1 Primary and secondary objectives

Our primary objective is:

- To obtain preliminary data about the effectiveness of a multi-component adherence support strategy to increase both ART and PrEP adherence during pregnancy and breastfeeding

Our secondary objectives are:

- To measure acceptability, feasibility, and fidelity of the separate components of the adherence support strategy in a “real world” setting
- To compare social harms between the intervention and control arms in the contexts of ART and PrEP
- To identify factors associated with successful ART and PrEP adherence among pregnant and breastfeeding women

Our exploratory objective is:

- To measure the incidence of maternal HIV infection among HIV-negative women on PrEP

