8.2.1 Integrated Next Step Counseling

Integrated next step counseling (iNSC) is a structured, patient-centered approach informed by motivational interviewing techniques.^{71,72} The goal of iNSC is to foster an environment for joint-problem solving in order that the participant may identify their individual needs to increase or sustain sexual health through biomedical and non-biomedical approaches. iNSC frames the counselling sessions as a non-judgmental discussion to explore the facilitators and challenges to sexual health and medication adherence. Through this process the participant is able to identify needs to optimize sexual health protection and medication adherence.

Study staff will be trained to provide iNSC to participants randomized to the intervention arm. iNSC uses eight distinct stages to guide the counselor and patient through a semi-structured discussion: introduce, review, explore, tailor, identify, strategize, plan, and document. Within each, the counselor guides the patient through motivational interviewing and other patient-centered strategies. iNSC will be provided at each scheduled study visit by trained study personnel. A standard case report form is used to document steps included in the discussion, as well as important content emerging from exploration of facilitators, challenges, needs and strategies.

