8.2.2 Adherence supporter training

There is a broad body of knowledge showing that peer or partner support can help to enhance adherence and retention in antenatal and HIV programs.⁴⁰ We propose an adherence supporter intervention. Participants will be asked to identify a partner, family member, or friend to whom they are willing to disclose their HIV status (for HIV-positive women) or their intent to initiate PrEP (for HIV-negative women). Participants may also select a clinic-based peer to serve in this adherence supporter role. Study staff will provide training for this adherence supporter in the month following enrollment, using materials adapted from similar interventions. A second “refresher” session will be provided the following month as well. The emphasis of these trainings will be basic HIV knowledge, importance of antiretroviral adherence, potential drug side effects, and practical strategies for supporting adherence. Based on our formative research, we believe the addition of this adherence supporter intervention to iNSC will help to reinforce behaviors discussed during patient-centered counseling.

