APPENDIX 1:

Schedule of evaluations for Trial 1 – adherence support for ART

	Clinic visits				Pharmacy visit	Pregnancy outcome
	Enrollment	Month 1	Month 3	Month 6	Monthly	6 weeks postpartum
Laboratory studies						
HIV RNA (viral load)	6 mL		6 mL	6 mL		
Hemoglobin	2 mL					
Syphilis screening	2 mL*					
Urine dipstick	X		X	X		
Vaginal microbiome	X	X				
Storage for HIV resistance testing	6 mL**			6 mL **		
Medical exam						
Medical history	X					
Obstetric exam	X	X	X	X		
Questionnaires						
Demographic information	X					
Sexual history	X			X		
Partner information	X		X	X		
Social harms (including IPV)	X	X	X	X		
Stigma	X			X		
Self-efficacy	X			X		
Depression	X			X		
HIV risk behaviors	X	X	X	X		
Delivery information						X
Study drug						
ART dispensed at PMTCT clinic					X	
Pill counts					X	
Self-report adherence					X	
Intervention assessment (Intervention arm only)						
Integrated next step counseling (iNSC)	X	X	X	X		
Adherence supporter	X					
Qualitative interviews (subset)	X***		X***	X***		

* will perform test if no results available in the medical record

** storage of leftover specimen for HIV resistance testing

*** schedule additional procedures within 30 days of visit for subset of participants enrolled in this component

Schedule of evaluations for Trial 2 – adherence support for PrEP

	Screening	Clinical visits			Pharmacy visit	Pregnancy outcome	HIV confirmatory testing
		Enrollment	Month 1	Month 3	Month 6	Monthly	6 weeks postpartum
Laboratory studies							
Rapid HIV antibody test	X	X		X	X		
Hepatitis B Antigen	4 mL						
ALT		2 mL					
Creatinine		2 mL		2 mL	2mL		
Syphilis screening		2mL *					
Urine dipstick		X	X	X	X		
Tenofovir concentration				4 mL	4 mL		
Vaginal microbiome		X	X				
HIV RNA (viral load)							4 mL
Storage for HIV resistance testing							6 mL
Medical exam							
Medical history	X						
Obstetric exam	X	X	X	X	X		
Questionnaires							
Demographic information		X					
Sexual history		X				X	
Partner information		X		X	X		
Social harms (including IPV)		X	X	X	X		
Stigma		X				X	
Self-efficacy		X				X	
Depression		X				X	
HIV risk behaviors		X	X	X	X		
Delivery information							X
Drug dispensation and adherence assessment							
PrEP dispensation						X	
Pill counts						X	
Self-report adherence						X	
Intervention assessment (intervention arm only)							
Integrated next step counseling (iNSC)		X	X	X	X		
Adherence supporter		X					
Qualitative interviews		X***		X***	X***		

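### Social harms count only if caused by study participation, so the by-arm incidence mixes true harm with attribution that can differ between the arms

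*Combined protocol and SAP*

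**What the plan says.** Section 8.10 (Safety Monitoring) makes causation part of the case definition: "A social harm will be defined as a non-medical untoward consequence of study participation". The adverse-event definition that follows does the opposite, counting events "whether or not considered related to participation in the research". A later sentence in 8.10 requires adverse events and social harms alike to be "assessed for seriousness / severity, expectedness, and relatedness".

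Section 6.1 lists as a secondary objective: "To compare social harms between the intervention and control arms in the contexts of ART and PrEP". Sections 6.2.2 and 6.2.4 name the incidence of social harms, in both arms, as a secondary outcome. Section 8.15.4 estimates that incidence within each arm and lists individual events; it gives no risk difference or confidence interval for social harms. The Protocol Summary words the outcome more narrowly, as harms linked to the study intervention.

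The arms differ in exposure. Under 8.2.2, intervention participants choose a supporter to whom they will disclose their HIV status or their plan to start PrEP. Under 8.2.3, control participants receive obstetric and newborn-care information and have no supporter. On staffing, 8.2.1 says: "Study staff will be trained to provide iNSC to participants randomized to the intervention arm". Section 8.10 gives the evaluation of social harms to study staff as well.

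Appendix 1 schedules a questionnaire on social harms, including intimate partner violence, at enrolment and months 1, 3 and 6 in each trial. It stands outside the block reserved for the intervention arm.

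**The concern.** A comparison of incidence between arms is interpretable only if the same event has the same chance of being counted in each arm. When an event must first be judged a result of taking part, that chance depends on how readily someone can link it to the study. An intervention participant whose partner reacts badly after a study-prompted disclosure has an obvious link. A Trial 1 control participant, collecting routine ART from the local PMTCT programme, may report the same conflict and have it put down to her HIV status.

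The documents do not use the word unblinded. However, they describe no masking, and participants and the staff who deliver counselling or train supporters must know the assignment. Nothing says who decides attribution, or by what rule.

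At stake is a secondary objective on possible harm from an intervention that relies on disclosure. The result also matters in the favourable direction: Table 2 maps partner violence, fear of stigma and fear of disclosure to both intervention components, so a reduction in background harm is a plausible effect that an attributed count would register poorly.

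**Working it through.** **Text against text.** (a) If every social harm is by definition caused by participation, grading its relatedness adds nothing; if the grading is meant to inform, unrelated harms must first be recorded. The two instructions in 8.10 do not fit together. (b) A questionnaire at enrolment suits an all-cause measure with a baseline and fits poorly with a measure of harm caused by taking part. (c) No sentence in 8.15 says whether incidence comes from the questionnaire or from events meeting the 8.10 definition.

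**Arithmetic.** The plan states no rate, power or precision for social harms, so there is no figure to reproduce. Inputs from the documents: 50 per arm in Trial 1 (8.14.1), 100 per arm in Trial 2 (8.14.2), and 95% confidence intervals without multiplicity adjustment (8.15.1). Harm rates and attribution probabilities are assumptions.

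Observed rate = true harm rate × probability of attribution. With the same true rate h in both arms, the observed difference (intervention minus control) is h × (attribution in intervention − attribution in control), although the true difference is 0.

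The last two columns give the chance that a 95% Wald interval for the risk difference excludes 0, by exact binomial enumeration. This is a yardstick only, since 8.15.4 names no such interval for this outcome.

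| True harm, both arms | Attribution, control / intervention | Observed, control / intervention | Difference (points) | Excludes 0, 50 per arm | Excludes 0, 100 per arm |
|---|---|---|---|---|---|
| 20% | 50% / 50% | 10% / 10% | 0 | 5.9% | 5.2% |
| 10% | 20% / 50% | 2% / 5% | +3 | 10.3% | 20.3% |
| 20% | 20% / 50% | 4% / 10% | +6 | 24.2% | 40.4% |
| 30% | 20% / 50% | 6% / 15% | +9 | 33.8% | 56.6% |
| 20% | 20% / 80% | 4% / 16% | +12 | 57.3% | 84.6% |
| 20% | 80% / 50% | 16% / 10% | −6 | 15.6% | 24.5% |

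Third row in full: 0.20 × 0.20 = 0.04 and 0.20 × 0.50 = 0.10, or 2 against 5 expected events with 50 per arm. Last row: 0.20 × 0.80 = 0.16 and 0.20 × 0.50 = 0.10, so the sign reverses.

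A real difference can also vanish. True harm of 10% in control and 20% in intervention, with attribution of 80% and 40%, gives 0.10 × 0.80 = 0.08 and 0.20 × 0.40 = 0.08.

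The bias scales with h. If harm is rarer than assumed, for instance because 8.3 excludes women whom staff judge to be at risk of violence or social harm from taking part, the absolute distortion shrinks in proportion.

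**The case against.** The strongest defence is that attribution-free data are already being collected. The Appendix 1 questionnaire covers violence and social harms at baseline and follow-up, stigma is measured at enrolment and month 6, and relatedness grading makes sense only if unrelated events are recorded. Section 8.15.4 promises detailed analysis plans before analysis, and 8.15.1 stresses estimation over testing in a pilot. On this view the defect is one loose sentence.

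Part of this stands: the data probably allow a sound comparison. It does not cure the defect, because the written definition excludes unattributed events and no analysis text uses either source to count them.

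The defence also rules out several stronger readings that a reader might infer:

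- *Control events fall to zero by construction.* They need not. Section 9.5 foresees harm to any participant whose involvement becomes known, and 8.9 provides for home visits irrespective of arm.
- *Both trials are affected equally.* In Trial 2 both arms receive study-supplied PrEP (8.6.2, 8.8.2), so control participants also have a visible link to the study.
- *Unattributed violence is never recorded.* Violence causing injury would still be an adverse event under 8.10.
- *A protective effect cannot be seen.* It could be seen in the questionnaire data, if they are analysed that way.
- *This is the main safety question.* No text says so; it is one of three secondary objectives.

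**Conclusion.** The point holds as a defect of outcome definition that should be corrected before the analysis plans are finalised. Followed as written, 8.10 yields a by-arm incidence that combines true harm with attribution, and attribution can differ by arm because only one arm has a study-prompted disclosure. It goes too far to say that the comparison reflects attribution instead of harm, or that it must show an excess in the intervention arm: the documents fix neither direction nor size.

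Across the assumed values with equal true harm, the spurious difference runs from −6 to +12 percentage points. Those figures show what unequal attribution can do; they do not predict what will happen in these trials. The effect is likely to be smaller in Trial 2. That staff and participants know the arm is inferred from the nature of the intervention and the absence of any masking. That a comparison is planned rests on the objective in 6.1, since 8.15.4 only estimates incidence within arms.

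**What to change.** 1. In 8.10, define a social harm as any reported relationship difficulty, partner violence, stigma or discrimination since the last visit, whatever its perceived cause, in line with the adverse-event definition. Grade relatedness afterwards, and state who grades it and whether they know the arm.
2. In 8.15.4, take the by-arm comparison from the all-cause follow-up answers to the existing questionnaire in both arms, with the enrolment answer as baseline. Give the enrolment question its own look-back period, since it has no previous visit to refer to.
3. List harms judged related to participation separately, for oversight.
4. Align the outcome wording in the Protocol Summary with 6.2.2 and 6.2.4.

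The cost is a few sentences and matching form wording; visits and instruments stay as they are. The questionnaire items are not in the documents, so check that they do not themselves ask only about study-caused harm. The downside is small: raw counts will be higher because they include background events.
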